5.3.1 Demographics and other baseline characteristics

Descriptive statistics of demographics and other baseline characteristics (e.g. efficacy variables at parent trial baseline and ECZTEND baseline [age, sex, ethnicity, race]) and the latest treatment regimen in the parent trial (placebo, tralokinumab, tralokinumab + TCS) will be presented for the SAF and by tralokinumab-naïve/re-treated/continuously treated subjects in the SAF. For the re-treated and continuously treated subjects, the presentation will further

be divided by responder/non-responder status in the parent trial; clinical response is defined as achievement of IGA 0/1 or EASI75 at the last assessment in the parent trial.

In addition, due to variable country closures due to by the commercialization of tralokinumab, the above defined descriptive statistics will be made for those subjects still ongoing in trial (i.e. those who have neither withdrawn nor completed the trial) at weeks 56, 104, 152, 216, and 264 relative to ECZTEND baseline for the SAF.

The above will also be made for subjects transferring in from LP0162-1334. However, only presenting summaries of the total, tralokinumab naïve, re-treated, and continuously treated, not the washed-out subjects.

5.3.2 Medical, Skin, and Atopic disease histories

Medical, skin, and atopic disease histories will be presented for the SAF.

The above will also be made for subjects transferring in from LP0162-1334. However, only presenting summaries of the total, tralokinumab naïve, re-treated, and continuously treated, not the washed-out subjects.

5.4 Disposition of subjects, medication, procedures, and exposure

5.4.1 Disposition of subjects

The reasons for withdrawal from the trial will be presented for the SAF, using the Aalen-Johansen cumulative incidence function estimator, over both the treatment period and the safety follow-up period.

In addition, reasons for withdrawal from the trial and reasons for permanent discontinuation of IMP will also be presented in the same manner over the treatment period for the SAF.

A stacked bar plot will be made showing the proportion of subjects in each region ongoing in the trial (i.e. those who have neither withdrawn nor completed the trial) over the treatment period and the safety follow-up period for the SAF.

The above will also be made for subjects transferring in from LP0162-1334. However, only presenting summaries of the total, tralokinumab naïve, re-treated, and continuously treated, not the washed-out subjects.

5.4.2 Concomitant medication and concurrent procedures

Concomitant medication at ECZTEND baseline will be presented for the SAF.

Concomitant medication in the treatment period will be presented for the SAF.

All concomitant medications and concurrent procedures will be listed.

The above will also be made for subjects transferring in from LP0162-1334. However, only presenting summaries of the total, tralokinumab naïve, re-treated, and continuously treated, not the washed-out subjects.

5.4.3 Extent of exposure and treatment compliance

Exposure

Exposure to treatment will be presented for the SAF as days of exposure in total, by exposure time cutoffs, and by parent trial.

Days of exposure will be calculated as the number of days from the date of the first IMP dose in ECZTEND to the date of the end of treatment visit, or – if the end of treatment visit is missing – to the date of permanent discontinuation of IMP.

Treatment compliance

Adherence will be presented for the SAF.

The above will also be made for subjects transferring in from LP0162-1334. However, only presenting summaries of the total, tralokinumab naïve, re-treated, and continuously treated, not the washed-out subjects.

5.5 Primary analysis

The primary endpoint in this trial is the number of adverse events during the treatment period from baseline up to Week 268, and the analysis of this endpoint is covered in the safety analysis section.

5.6 Efficacy analysis

All efficacy endpoints will be analysed using the FAS. In addition, to support the secondary objective of the trial, all efficacy analyses will be done by tralokinumab-naïve, re-treated, and continuously treated, and in addition for the washed-out subgroup (Section 7.1).

5.6.1 Analysis of Secondary endpoints

For definitions of endpoints see Panel 1.

5.6.1.1 Binary endpoints

5.6.1.1.1 Primary analysis

Observed cases analysis by each scheduled visit will be performed, presenting proportions with a 95% Wilson CIs.

Figures will be made of the observed proportions of responders by visit with CI and a table appended showing the number of subjects with observed data and number of subjects who have not dropped out at each visit.

5.6.1.1.2 Sensitivity analyses

The strategies used in these sensitivity analyses use hypothetical assumptions to investigate potential survival bias and do not necessarily represent the truth if all subjects had continued. The goal is to provide multiple hypothetical scenarios, of which some will reflect extreme assumptions and some will be closer to the expected true estimate. Examining both extreme and realistic hypothetical scenarios should allow for a reasonable discussion of where the true estimate is.

All analyses will be presented by all planned assessments with 95% Wilson CIs, and where data is being multiply imputed, Rubin's rule will be applied using Lott and Reiter's formula for Wilson CIs with MI (1).

5.6.1.1.2.1 Hypothetical MI of missing data and any unobserved data (hMI)

This sensitivity analysis seeks to mitigate possible survival bias by estimating the response if all subjects had continued in the trial like they were before they dropped out.

The proportion of responders will be calculated by each scheduled visit based on both observed, and multiply imputed missing or unobserved assessment data. The missing assessment data will be imputed using a 2-step MI strategy involving both a regression-based approach imputing data up to the 1st year (Week 56 visit) in the trial and a within-subject approach imputing data after the 1st year in the trial. For the complete technical definition of the 2-step MI strategy please see section 5.6.1.1.2.3. The split at 1 year was chosen for several reasons:

 Subjects will enter the trial differently, some being untreated or washed-out of tralokinumab and others may be under continuous treatment with tralokinumab when starting the trial. A visit-sequential full conditional specification regression-based approach is ideal to reflect this expected change over time in the overall proportion of response.

- Survival bias affecting the proportion of responders can within reason be mitigated/minimized provided suitable adjustment in the 1st year. This is because a sizable part and broadly defined population were followed-up without interruptions during the first year.
- 3. After 1 year, the population can be assumed to have regressed to its mean while under continuous treatment with tralokinumab.

This hypothetical assumption applied to the imputation of missing data from subjects who either completed treatment (e.g. due to commercialization of tralokinumab in their country) or permanently discontinued IMP is strong. However, assuming that these subjects continued as if they had regressed to their within-subject mean is appropriate under this hypothetical sensitivity scenario as it attempts to estimate the proportion of responders under minimal influence of survival bias.

5.6.1.1.2.2 mNRI-MI with treatment adherence MI strategy (mNRI-MI-Hyp)

This sensitivity analysis seeks to estimate a lower bound of the response by estimating the response achieved without permanent discontinuation of IMP due to LoE or AE if all subjects who withdrew for other reasons had continued in the trial like they were before they dropped out.

The response at each scheduled visit will be calculated based on both observed and multiply imputed missing or unobserved assessment data, with those having permanently discontinue IMP due to LoE or AE prior to the analysed visit imputed as non-responders. Missing assessment data will be imputed using the same 2-step MI strategy (see section 5.6.1.1.2.3) as in the hMI sensitivity analysis. Permanent discontinuations of IMP due to LoE or AE of subjects who permanently discontinued IMP for other reasons or completed the trial will be imputed using the hypothetical treatment adherence MI strategy (see section 5.6.1.1.2.3) onto subjects who either completed treatment or permanently discontinued IMP for other reasons than LoE or AE after the time they discontinue.

This hypothetical scenario sets out to estimate a lower bound of efficacy by assuming that subjects who are either observed or imputed to permanently discontinue of IMP due to LoE or AE are perpetually considered non-responders. In dealing with subjects who drop-out early, it sets a strong assumption that regression-to-the-mean can be assumed when imputing assessment data. But in doing so, this sensitivity strategy targets the same underlying target of estimation established in trials of other similar drugs in AD long-term extension trials (2) where subjects have been non-responder imputed based only on observed permanent discontinuation of IMP due to LoE or AE, with assessment data imputed using last

observation carried forward. However, last observation carried forward will not be used as it is not appropriate, see e.g., "Fallacies of Last Observation Carried Forward" (3).

5.6.1.1.2.3 Imputation strategies

2-step MI strategy

A 2-step MI strategy will be employed to mitigate potential survival bias as reasoned above. MI of missing data and data unobserved after intercurrent events can be used by the different sensitivity analyses per the need of the various estimation requirements:

- Data up until the Week 56 visit will be imputed using a Full Conditional Specification gaussian regression-based MI model adjusting for previous visit (if planned visit exist), next visit (if planned visit exist), parent trial, and region. If the score being imputed is ordinal or binary, an ordinal logistic regression model will be used instead. The assumption here is that the data used in the MI regression model are robust enough.
- 2. Data after the Week 56 visit will be imputed using a within-subject non-parametric approach leveraging the proportion of response each subject has achieved estimated using linear interpolation across observed and (in the previous step) imputed scores. This proportion of response could also be called a within-subject AUC of days in response. The imputation will be derived in the following 3 steps:
 - 1. All days between observed and imputed visits will be imputed on the assessment's scale by using linear interpolation between visits. For binary and ordinal scores, the imputed value will be rounded.
 - 2. Then all days will be transformed into the binary endpoint and an average of those 1s (response) and 0s (non-response) going one year back (but not further back than the Week 16 visit) will be the AUC of days in response. This assumes that from the Week 16 visit that all subjects have regressed to their individual mean while under long-term treatment with tralokinumab (due to the safety follow-up between parent trials and ECZTEND with no dosing).
 - 3. An imputed response at each day, including planned visits, after the intercurrent event will then be drawn from the Bernoulli distribution by using the AUC of days in response as a probability.

Hypothetical treatment adherence MI strategy (Hyp)

MI of treatment adherence status at end of the treatment period, t_{EoTrt} , for subjects experiencing an intercurrent event, at time t_{ICE} , will be imputed based on the semi-parametric Cox proportional hazard model. The model will provide an estimated probability $\hat{p}(t_{EoTrt},$ region, parent trial) of being on treatment at the later time t_{EoTrt} conditional on being on

treatment at the earlier time t_{ICE} in the hypothetical scenario where permanent discontinuation of IMP due to pandemic restrictions would not occur. The conditional probability \hat{p} will be calculated as the estimated survival function evaluated at t_{EoTrt} divided by the same function evaluated at time t_{ICE} (with $t_{ICE} < t_{EoTrt}$) and imputed using random draws from an exponential distribution with rate \hat{p} . For specific regional analyses, t_{EoTrt} may vary depending on the scarcity of data at the end the treatment period, but for summaries of the main populations Week 264 will be used.

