5.9 Interim analysis

At the time of writing this SAP several analyses have been conducted. Mainly, an interim report was prepared for EMA which delivered a comprehensive analysis focused solely on safety analyses. Japanese subjects in ECZTEND have been analysed for submission to PMDA. Several abstracts, posters, oral presentations, and articles have been presented and/or published featuring analyses from ECZTEND both in terms of safety and efficacy analyses on differing data-cuts.

6 Changes to analyses described in the protocol

Panel 5 summarises the changes to the analyses planned in the protocol.

Panel 5: Changes to the analyses described in the CTP

Section in the CTP	Description of change	Brief rational3
14.3.5	The specified strict NRI sensitivity analysis has been replaced by 2 sensitivity analyses.	The specified sensitivity analysis was not reasonable as it was not possible to distinguish causes based on the original intent, and due to the amendment extending the trial causing some subjects to not consent to continuing in the trial. A modified NRI method has been introduced as a replacement together with appropriate MI method.
14.3.5	No split on response vs non-response based on the last assessment in parent trials.	The last assessment is not necessarily representable of a fluctuating disease like AD and is conditioned by a lot of other factors, e.g. differing parent trial treatment periods and procedures.

Abbreviations: AD = atopic dermatitis; CTP = clinical trial protocol; MI = multiple imputation; NRI = non-responder imputation.

7 Supporting documentation

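### SAP 5.6.1.1.2.2 presents mNRI-MI-Hyp as a lower bound of IGA 0/1 and EASI75 response, but true response can lie below it, and no planned analysis counts every non-completer withdrawal as non-response

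*SAP*

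**What the plan says.** The main analysis of the two secondary endpoints is observed cases by visit (SAP 5.6.1.1.1). Two imputed sensitivity analyses accompany it, hMI and mNRI-MI-Hyp. Of the second the SAP says: "This sensitivity analysis seeks to estimate a lower bound of the response". The last paragraph of the same section repeats the lower-bound aim.

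The rule for failures is that "subjects who are either observed or imputed to permanently discontinue of IMP due to LoE or AE are perpetually considered non-responders". For everyone else the target is the response "if all subjects who withdrew for other reasons had continued in the trial like they were before they dropped out". Under SAP 5.6.1.1.2.3, missing data up to Week 56 come from a regression model. After that, each response "after the intercurrent event will then be drawn from the Bernoulli distribution by using the AUC of days in response as a probability", where the AUC is the subject's own share of days in response over at most the past year. A later LoE/AE discontinuation may also be drawn for completers and other-reason leavers.

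On output: "All analyses will be presented by all planned assessments with 95% Wilson CIs". For the adherence draw, "for summaries of the main populations Week 264 will be used" as the time horizon.

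Protocol 14.3.5 treated withdrawn subjects as non-responders in the FAS analysis and stated this as a consequence of the stopping rules. SAP Section 6, Panel 5 records the change: "The specified strict NRI sensitivity analysis has been replaced by 2 sensitivity analyses". The reasons given are that "it was not possible to distinguish causes based on the original intent" and that some subjects did not consent to the extension.

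**The concern.** A lower bound is a value that the true rate cannot fall below. An analysis that gives other-reason leavers their own earlier on-treatment response does not have that property. It is a point estimate under the assumption that leaving carried no information about later response, apart from the drawn LoE/AE failures.

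The observed-case analysis keeps only subjects who still attend, so it may flatter late visits. mNRI-MI-Hyp is the only planned check on the low side. A reader who takes the label literally would conclude that late IGA 0/1 and EASI75 rates cannot be lower than shown. With the protocol's rule replaced, no planned analysis shows the response if all non-completer withdrawals had lost it.

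**Working it through.** There is no plan figure to reproduce: neither document gives a response rate, a withdrawal rate or a value for the bound. All rates below are assumptions, except the total of about 1,600 subjects (Protocol 14.1).

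**1. Decomposition at one visit.** Let *n_o* be subjects observed with response rate *r*, *w1* LoE/AE withdrawals, *w2* other-reason withdrawals with prior response *p2*, *c* completers with prior response *pc*, and *s* the chance of not being drawn as an LoE/AE failure.

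- mNRI-MI-Hyp = [*n_o·r* + *s*(*w2·p2* + *c·pc*)] / (*n_o* + *w1* + *w2* + *c*)
- True rate with LoE/AE counted as failure: replace *s·p2* and *s·pc* by the response these subjects would really have had.

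The estimate is too high as soon as the other-reason leavers' real response falls below *s·p2* (taking *c* = 0).

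**2. Illustration.** *n_o* = 1,200, *r* = 0.80, *w1* = 120, *w2* = 280, *p2* = 0.60, *c* = 0, *s* = 0.95.

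- mNRI-MI-Hyp: (960 + 280 × 0.95 × 0.60) / 1,600 = 1,119.6 / 1,600 = 70.0%
- Break-even: 0.95 × 0.60 = 57%
- Leavers really respond at 40%: (960 + 112) / 1,600 = 67.0%
- Leavers really respond at 20%: (960 + 56) / 1,600 = 63.5%
- All withdrawn as non-responders: 960 / 1,600 = 60.0%

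Suppose the target is instead response if everyone had continued, with the 120 LoE/AE leavers responding at an assumed 20%. At a 40% rate in the other leavers the truth is (960 + 112 + 24) / 1,600 = 68.5%, still below 70.0%.

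**3. Simulation at Week 248** (40,000 subjects, 25% other-reason and 8% LoE/AE withdrawal, worsening from about 8 weeks before an other-reason exit, on a latent scale).

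| Worsening | mNRI-MI-Hyp | True rate (LoE/AE as failure) | Difference |
|---|---|---|---|
| none | 62.4% | 63.3% | -0.9 |
| 0.5 | 62.3% | 60.7% | +1.6 |
| 1 | 61.7% | 57.7% | +4.0 |
| 2 | 60.8% | 52.6% | +8.2 |
| 3 | 60.4% | 49.3% | +11.1 |

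Without worsening the method is about right. With any worsening tested it lies above the truth.

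**4. Order of the scenarios.** mNRI-MI-Hyp cannot exceed hMI when both use the same imputed assessments, because it only turns responses into non-responses. Counting all withdrawn subjects as non-responders (NRI) gives a value at or below mNRI-MI-Hyp when completers are excluded from both or handled alike in both: there were no violations in 20,000 random configurations. If NRI drops completers while mNRI-MI-Hyp keeps and imputes them, the order reversed in 21% of those configurations, a share that depends on arbitrary ranges.

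It can also reverse if completers are imputed in both but face the failure draw only in mNRI-MI-Hyp. With *o* the share of other-reason leavers, *R* their prior response, *a* the chance of no drawn failure, *c* now the completer share and 0.6 the completers' response, mNRI-MI-Hyp minus NRI is *o·R·a* − *c* × 0.6 × (1 − *a*). This runs from 0.1 × 0.4 × 0.68 − 0.6 × 0.6 × 0.32 = -8.8 points to 0.3 × 0.6 × 0.95 − 0.3 × 0.6 × 0.05 = +16.2 points.

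**5. Why the imputed share matters.** The protocol synopsis caps treatment at 114 weeks for LP0162-1334, so 5 of the 9 secondary timepoints (136, 152, 184, 216, 248) come later. It caps non-re-consenters at 140 weeks, so 4 of 9 come later. Both imputed analyses still report these visits.

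**The case against.** The strongest reply is that the risk is smaller than the algebra suggests. SAP 5.2 says that withdrawals by the subject, losses to follow-up and other reasons were queried to rule out an underlying LoE or AE. mNRI-MI-Hyp goes wrong mainly when hidden failures sit among the other-reason leavers, which is what the query screens for. SAP 5.6.1.1.2 also calls the scenarios hypothetical and not necessarily true, and 5.6.1.1.2.2 calls its imputation assumption strong. All of this stands. It makes overshoot less likely, but it does not turn the estimate into a bound.

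The replacement of the protocol rule was disclosed with reasons, and a SAP update is a route that Protocol 14.3.11 allows. A reader might infer that a more conservative analysis was removed without explanation; the documents do not support that. The protocol tied the rule to the stopping rules, so counting LoE/AE as failure is a defensible reading of the original intent. Applied to the full FAS, the strict rule would also fail administrative completers if they stayed in the denominator.

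Much of the reporting is already planned: observed and not-dropped-out counts under the observed-case figures (SAP 5.6.1.1.1) and Aalen-Johansen curves by reason (SAP 5.4.1). A careful reader could work out the unobserved share by subtraction. It is not shown beside the imputed estimates.

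Finally, the adherence draw is specified as exponential with the adherence probability as its rate and no time unit. I read it as intended, with that probability being the chance of staying on treatment. Taken literally in days or weeks, *s* would be near 0 well after exit and mNRI-MI-Hyp would fall towards NRI.

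**Conclusion.** The stated property is wrong: mNRI-MI-Hyp is a hypothetical scenario at or below hMI, not a lower bound. In the illustration it exceeds the true rate by 3.0 or 6.5 points (70.0% against 67.0% or 63.5%). The real excess cannot be known from the documents and may be nil if other-reason leavers would have continued unchanged.

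Two stronger readings are tempting and not supported. One is that the protocol's rule always lies at or below mNRI-MI-Hyp. That holds only with completers excluded or handled alike, and the protocol does not say how completers' later visits are treated. The other is that the distance to NRI measures the error. Among subjects whose planned treatment reaches the visit, that distance is *o·R·a*, from 0.1 × 0.4 × 0.68 = 2.7 to 0.3 × 0.6 × 0.95 = 17.1 points under assumed inputs. But NRI assumes no response in any leaver, so this is a range between scenarios.

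No test is planned (SAP Section 2) and the primary endpoint is safety. What is affected is how late IGA 0/1 and EASI75 rates may be described. The correction should be made and is cheap.

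**What to change.** 1. In both places in SAP 5.6.1.1.2.2, replace *lower bound* with *a hypothetical scenario at or below hMI that counts LoE/AE discontinuation as non-response*.

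2. Beside each hMI and mNRI-MI-Hyp estimate, show the percentages of subjects observed and imputed at that visit.

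3. Add one conservative scenario. Take SAP 5.2 treatment completers out of numerator and denominator after completion. Limit withdrawn and continuing subjects alike to those whose planned treatment reaches the visit. Count all other withdrawals as non-response. Label it conservative, not a bound, and report the gap between scenarios as a sensitivity range, not as the error of mNRI-MI-Hyp.

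The first two items cost wording and table columns. The third needs programming from entry dates, planned end dates and the existing classification, and its limits must be stated. It relies on the 17-day proxy for some completers, because non-consent to the extension was not collected. Late denominators become smaller. It is also biased downwards after May 2021, because it is unknown whether earlier withdrawals would have re-consented. With *w* the share of earlier withdrawals (10–20%), *r* the re-consent rate (50–90%) and response 0.75 in those remaining, all assumed, the bias is 0.75(1−*w*) − 0.75(1−*w*)*r* / [(1−*w*)*r* + *w*]. That runs from 0.675 − 0.6075/0.91 = 0.7 points to 0.60 − 0.30/0.60 = 10.0 points.

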5.2 Intercurrent events

The following intercurrent events are defined to describe the treatment effect that is targeted with the different estimand strategies described underneath.

- Treatment completion: This intercurrent event occurs either when a subject completes the period of the trial the subject consented to or is withdrawn from the trial due to tralokinumab becoming commercially available in their country. This intercurrent event is introduced mainly due to the extension amendment introduced in May 2021. Notably, it was not collected in the eCRF whether a subject withdrew due to not consenting to continue in the extension of the trial. Subsequently, an algorithm was built such that withdrawals close (17 days) to the country-specific closure date were classified as treatment completers instead of as having permanently discontinued IMP. See the ADRG for a complete algorithm defining treatment completion.
- **Permanent discontinuation of IMP:** This intercurrent event occurs when a subject is withdrawn from trial while under treatment. It can occur at the subjects' own initiative, at the discretion of the investigator or the sponsor, or if the subject is lost to follow-up:
 - **Due to lack of efficacy (LoE) or adverse event (AE):** This intercurrent event occurs when it is specified that the primary reason for withdrawal from trial while under treatment is due to either LoE, or AE. Of note, the reasons "withdrawal by subject", "lost to follow-up" and "other" were queried to ensure that the underlying reason was not LoE or AE.
 - Not due to LoE nor AE: the complement to the previously specified reasons.

5.3 **Baseline presentations**

Due to safety-related analyses specified for subjects coming from the LP0162-1334 trial in the protocol, baseline presentations will be specified where applicable for subjects from the LP0162-1334 trial.

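### The treatment-adherence imputation for mNRI-MI-Hyp is defined as staying on treatment with only pandemic stops removed, not as freedom from discontinuation due to LoE or AE, which is the event it is meant to impute

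*SAP*

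**What the plan says.** SAP 5.2 names treatment completion and two kinds of permanent discontinuation of IMP: due to LoE or AE, and the remainder ("Not due to LoE nor AE: the complement to the previously specified reasons"). No pandemic-related event is defined.

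SAP 5.6.1.1.2.2 states what mNRI-MI-Hyp has to impute: "Permanent discontinuations of IMP due to LoE or AE of subjects who permanently discontinued IMP for other reasons or completed the trial will be imputed". The consequence is non-response, "with those having permanently discontinue IMP due to LoE or AE prior to the analysed visit imputed as non-responders". The purpose is also stated: "This hypothetical scenario sets out to estimate a lower bound of efficacy".

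SAP 5.6.1.1.2.3 then describes the strategy. Treatment adherence status "will be imputed based on the semi-parametric Cox proportional hazard model" with region and parent trial. The model supplies the probability "of being on treatment at the later time" t_EoTrt, given that the subject was on treatment at t_ICE, "in the hypothetical scenario where permanent discontinuation of IMP due to pandemic restrictions would not occur". That probability, p̂, is the ratio of the estimated survival function at the two times. Status is then "imputed using random draws from an exponential distribution with rate" p̂. For the main populations t_EoTrt is Week 264.

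**The concern.** The two subsections name different events. A subject who leaves by choice, is lost to follow-up or is withdrawn for another reason is off treatment but has not stopped for LoE or AE. A probability of being on treatment that removes only pandemic stops still counts all those departures as failures. The analysis needs the chance of a later LoE/AE stop, because only that event should make a subject a non-responder.

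Read literally, the rule also conflicts with the aim in SAP 5.6.1.1.2.2. A subject observed to leave for another reason has responses imputed onwards as if treatment had continued, while a completer imputed to leave at an all-cause rate becomes a permanent non-responder.

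The main analysis of IGA 0/1 and EASI75 is observed cases (SAP 5.6.1.1.1), so the sensitivity analyses carry the question of survival bias. This is one of two. It is the modified non-responder analysis that replaces the protocol's rule (SAP section 6), and it is repeated in each treatment-history subgroup (SAP 5.6.1.1.3). SAP section 1 expects the text to be detailed enough for a reader to reproduce every analysis; here two programmers could code different events.

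**Working it through.** **Text against text**

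| Item | SAP 5.6.1.1.2.2 | SAP 5.6.1.1.2.3 |
|---|---|---|
| Event | Discontinuation due to LoE or AE | Ceasing to be on treatment |
| Scenario | Subjects who withdrew for other reasons had continued | No discontinuation from pandemic restrictions |
| Who is imputed | Completers and other-reason discontinuers | Subjects with an intercurrent event at t_ICE |
| Cox event and censoring | Not stated | Not stated |

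The withdrawal reasons in Protocol 10.2.2 and 11.8 are lack of efficacy, adverse event, withdrawal by subject, withdrawal by parent/guardian, lost to follow-up, death and other. None is pandemic-related. SAP 5.2 refers to the ADRG for the treatment-completion algorithm, not for this model.

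**What the event definition does to the conversion rate**

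The plan gives no figure for this step, so there is nothing to reproduce. What follows is an illustration.

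Inputs:
- t_EoTrt = Week 264 (SAP 5.6.1.1.2.3).
- t_ICE = Week 140, the longest treatment for subjects who stopped in May 2021 (Protocol synopsis).
- Constant annual hazards, assumed: LoE/AE h₁ = 2–8%; other reasons h₂ = 2–10%.

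Time at risk: d = (264 − 140)/52.1775 = 2.38 years.

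The SAP's ratio is p̂ = S(264)/S(140). The intended conversion to non-responder is 1 − p̂:
- LoE/AE only: 1 − exp(−h₁d)
- Any discontinuation: 1 − exp(−(h₁ + h₂)d)

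| h₁ | h₂ | LoE/AE only | Any discontinuation | Ratio |
|---|---|---|---|---|
| 2% | 2% | 4.6% | 9.1% | 1.95 |
| 2% | 10% | 4.6% | 24.8% | 5.35 |
| 5% | 5% | 11.2% | 21.2% | 1.89 |
| 8% | 2% | 17.3% | 21.2% | 1.22 |
| 8% | 10% | 17.3% | 34.8% | 2.01 |

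For h₁ = h₂ = 5%: 1 − exp(−0.05 × 2.38) = 11.2% and 1 − exp(−0.10 × 2.38) = 21.2%.

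Two other codings bracket these figures. If completion were also counted as leaving treatment, S(264) would fall close to zero and nearly every completer would be converted. If completion and other-reason discontinuation are censored, the ratio is the LoE/AE quantity that SAP 5.6.1.1.2.2 needs.

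**Effect of the written draw**

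Suppose the draw is an exponential time in years with rate p̂. In the 5%/5% case the chance of an event within d is:
- LoE/AE only: 1 − exp(−0.888 × 2.38) = 88%, against 11.2% intended.
- Any discontinuation: 1 − exp(−0.788 × 2.38) = 85%, against 21.2% intended.

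A higher probability of staying on treatment gives more conversions, the reverse of what is meant. Correcting the event alone therefore does not restore the intended rate.

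**The case against.** The strongest reply is that SAP 5.6.1.1.2.3 has to be read with the subsection that invokes it. SAP 5.6.1.1.2.2 names LoE/AE as the event and supposes that other-reason withdrawals had continued. Under that supposition the only way off treatment is LoE or AE, so being on treatment means having had no such stop, and the pandemic clause is stray wording. This is a fair account of the probable intent. It stands to this extent: a reader might infer that completers will in fact be converted at the wrong rate, and the documents do not establish that, because neither the event nor the censoring is stated. The reply does not remove the defect, since SAP 5.6.1.1.2.3 states its own, different scenario and says nothing to override it.

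A reader might also infer that pandemic-related stops cannot be identified at all. That goes too far. Protocol 10.2.2 requires a specification when the reason is adverse event or other, and Appendix 3K has COVID-19 reasons recorded for missed visits and doses, so some could be recovered. Even full identification would not help, because removing pandemic stops leaves every other non-LoE/AE reason in the event.

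Finally, the analysis is offered as a lower bound, and SAP 5.6.1.1.2 warns that some scenarios are extreme. An all-cause event loosens the bound and does not inflate efficacy. That limits the harm. But SAP 5.6.1.1.2.2 also claims the same target of estimation as earlier atopic dermatitis extension trials that imputed non-response only for observed LoE/AE discontinuation, and an all-cause event would break that comparability.

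**Conclusion.** The point holds as a contradiction in the specification. SAP 5.6.1.1.2.2 and 5.6.1.1.2.3 name different events, the pandemic scenario is neither defined in SAP 5.2 nor the one needed, and the Cox event and censoring are missing. Followed literally, with conversion taken as 1 − p̂, too many completers and other-reason discontinuers become non-responders and the lower bound is too low.

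The size for this trial cannot be computed. The illustration rests on constant, assumed hazards and departure at Week 140: 21.2% against 11.2% at 5% per year for each cause, and 9.1–34.8% against 4.6–17.3% over the assumed ranges. It leaves out the written exponential draw. A reader might turn these figures into a loss of percentage points in late response. The documents do not support that, because it also needs the share of subjects imputed and their response probability, neither of which is given.

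The scope is one of two descriptive sensitivity analyses of IGA 0/1 and EASI75. The observed-cases analysis, hMI and the primary safety endpoint are unaffected, and SAP section 2 specifies no testing. The correction is worth making before programming, but the trial's main results do not depend on it.

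**What to change.** In SAP 5.6.1.1.2.3:

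- Define the Cox event as permanent discontinuation of IMP due to LoE or AE, as classified in SAP 5.2.
- Censor treatment completion and discontinuation not due to LoE or AE at t_ICE, and state the assumption that this censoring is non-informative given region and parent trial.
- Delete the pandemic clause.
- Separately, replace the exponential draw with rate p̂. One option is to draw the LoE/AE event time from the conditional survival function S(t)/S(t_ICE), which also gives the status before each analysed visit that SAP 5.6.1.1.2.2 requires.

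The first three changes cost a few sentences and one event flag. The fourth needs a revised imputation step in the program. No new data are needed.
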